#### **13.3.3 Safety**

We will tabulate adverse events possibly, probably or definitely related to treatment as counts and percentage according to NCI Common Terminology Criteria for Adverse Events version 4.0 in Appendix II (see Section 10.1.1-10.1.5).

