#### 3.3.3. Randomization

Randomization of study subjects will be done in 3:1 ratio to the treatment arm and control arm. Due to the nature of study treatment, this is an unblinded study. A randomization list will be prepared by the SCCCBiostatistics and implemented by the research staff.

After each patient's study eligibility is confirmed and the informed consent is signed, the research staff will enter the required subject information into the CIERRA system in order to register the subject. The coordinator of the PI will receive the designated patient ID, study arm, randomization number, and randomization date. Coordinator will print the randomization confirmation form from the CIERRA system and place it in the subject's research chart and then notify the requesting member of the study team of the treatment assignment for the new randomized subject.

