### 10.1 Definitions

10.1.1 **Adverse events**(AE's) will use the descriptions and grading scales found in the NCI Common Terminology Criteria for Adverse Events (CTCAE v 4.0) in Appendix II.

**Adverse events:** Any unfavorable and unintended sign (including abnormal laboratory finding), symptom, or disease temporally associated with the use of a medical treatment or procedure, regardless of whether it is considered related to the medical treatment or procedure (attribution of unrelated, unlikely, possible, probable, or definite). Each AE is a unique representation of a specific event used for medical documentation and scientific analysis.

10.1.2 A **serious adverse event (SAE)** is defined by the federal regulations as any adverse event that:

- Results in death; or is
- Life threatening; or
- Results in permanent impairment of body function or permanent damage to a body structure; or
- An event requires medical or surgical intervention to prevent permanent impairment or damage to a body function or body structure.

SAE's are defined by FDA and therefore seriousness (not severity) serves as a guide for defining regulatory reporting obligations for patient/subject safety. **Serious** is based on patient/event outcome or action criteria usually associated with events that pose a threat to a patient's life or functioning.

The definition of serious adverse event (experience) also includes **important medical events**. Medical and scientific judgment should be exercised in deciding whether reporting is appropriate in other situations, such as important medical events that may not be immediately life-threatening or result in death or hospitalization but may jeopardize the patient or **may require intervention** to prevent one of the other outcomes listed in the definition above. These should also usually be considered serious. Examples of such events are intensive treatment in an emergency room or at home for allergic bronchospasm; blood dyscrasias or convulsions that do not result in hospitalization; or development of drug dependency or drug abuse.

10.1.3 **Expected events** are those that have been previously identified as resulting from administration of the agent. For this study, these include:

Likely:

- Pain of the skin
- Edema
- Erythema and/or purpura
- Temporary skin hypopigmentation or hyperpigmentation

Unlikely:

- Hematoma

- Scarring
- Herpes Simplex Virus outbreak if treating an area with past recurrent outbreaks, usually around the mouth

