#### 10.2.2 Steps to determine if an adverse event is to be reported in an expedited manner:

Step 1: *Identify the type of event using the NCI Common Terminology Criteria for Adverse Events (CTCAE) version 4.0.*

The CTCAE provides descriptive terminology and a grading scale for each adverse event listed. A copy of the CTCAE can be downloaded from the CTEP home page (<http://ctep.cancer.gov>). Additionally, if assistance is needed, the NCI has an Index to the CTCAE that provides help for classifying and locating terms. All appropriate treatment locations should have access to a copy of the CTCAE.

Step 2: *Grade the event using the NCI CTCAE.*

Step 3: *Determine whether the adverse event is related to the protocol therapy (investigational or commercial).*

Attribution categories are as follows: Unrelated, Unlikely, Possible, Probable, and Definite.

Step 4: *Determine the prior experience of the adverse event.*

Step 5: *Review Table 10.1 to determine if there are any protocol-specific requirements for reporting of specific adverse events that require special monitoring.*

Step 6: *Determine if the protocol treatment given prior to the adverse event included investigational agent(s), a commercial agent(s), or a combination of investigational and commercial agents.*

NOTE: If the subject received at least one treatment with the investigational device serious adverse events will be reported as indicated in section 10.3.

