## **13.0 STATISTICAL CONSIDERATIONS**

### **13.1 Study Design/Objectives**

This is a prospective, unblinded, randomized, two-arm (treatment arm vs Control/non-treatment arm) pilot study to determine whether the 595/1064 nm laser merits further study for efficacy in the treatment of basal cell carcinoma. The primary objective of the study is to preliminarily assess the efficacy of the 595/1064 nm multiplex laser for the treatment of superficial and

nodular basal cell carcinomas less than 1.5 cm in size. Our primary endpoint will be the overall response rates (CR+PR), as defined in section 9.0.

The secondary objective of this study is to assess the safety and side effect profile of the multiplex laser for this indication.

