### 13.2 Sample Size Justification/Accrual Rate

The analysis set (evaluable subjects) consist of study-eligible subjects who either complete three treatments/three study visits and the biopsy visitor are withdrawn from the study due to showing evidence of PD during the study (non-responder). Subjects will be non-evaluable when they do not wish to continue in the study, are unable to continue in the study, or they cannot complete treatments or study visits for any reason other than PD. There will be 15 evaluable subjects in the treatment arm and 5 evaluable subjects in the control (non-treatment) arm. We expect that three to four subjects in both treatment arm and control arm will be non-evaluable. Therefore, the planned maximum number of enrolled subjects will be 28. The number of subjects is small due to the preliminary nature of the study, yet similar in size to previous studies (Konnikov et al 2011 and Shah et al 2009), which only used the 595 nm laser. Out of our 15 subjects in the treatment arm, we expect eleven or more subjects will respond to proposed treatment (either CR or PR). The table below shows significance (p-value) of hypothetical study findings assuming one BCC per subject. As shown in the second row, if one out of five subjects in the control arm shows either CR or PR and twelve or more out of fifteen subjects in the treatment arm show either CR or PR then test of comparing proportions of two arms is statistically significant (p-value < 0.05). If none in the control arm show either CR or PR and nine or more out of fifteen subjects in the treatment arm have either CR or PR, we also get a statistically significant difference indicating a better response rate in the treatment arm.

Number of subjects (CR or PR) among 15 subjects in the treatment arm vs. 5 in control arm	p-value*
11 (73.3%) vs. 1 (20%)	0.058
12 (80%) vs. 1 (20%)	0.031
9 (60%) vs 0 (0%)	0.030

\* one-sided Fisher's exact test (assuming every subject has one BCC)

One to two subjects will be accrued per week secondary to availability of the laser.

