### APPENDIX I: STUDY CALENDAR

Procedure	Screening	Randomization 	Day 0	Day28 (+/- 7 days)	Day 56 (+/- 7 days)	Day 84 (+/- 7 days)	Day 91 (+/- 7 days)/ Follow up visit
Written Informed Consent	X						
HIPAA	X						
Photo consent	X						
Eligibility checklist 	X						
Velos	X						
Randomization		X					
Pt and lesion characteristics 			X	X	X	X	

Treatment #1 			X				
Treatment #2 				X			
Treatment #3 					X		
Photographs are taken			X	X	X	X	
Monitoring of adverse events and concomitant medication			X	X	X	X	X
Dermatologic eval for clearance						X	
Excisional biopsy						X	

Within 3 months of initial diagnostic biopsy and within 1 week of enrollment (+ 3 days)

 Source document titled "Enrollment"

 Source document titled "Patient information"

 Or regular study visit for control arm

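### The only planned safety table keeps just the events attributed to treatment in an open-label trial, and no safety population is named

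*Combined protocol and SAP*

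**What the plan says.** Section 13.1 states the aim: "The secondary objective of this study is to assess the safety and side effect profile of the multiplex laser for this indication". No other secondary objective is listed.

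Section 13.3.3 is the entire safety analysis: "We will tabulate adverse events possibly, probably or definitely related to treatment as counts and percentage", graded by CTCAE version 4.0. It specifies no layout by arm, no analysis population and no denominator.

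Collection is wider than this. Section 10.1.1 defines an adverse event as an unfavourable occurrence "regardless of whether it is considered related to the medical treatment or procedure". The Appendix I row "Monitoring of adverse events and concomitant medication" is marked at Days 0, 28, 56, 84 and 91. Sections 5.2 and 5.3 have subjects in both arms asked about events.

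On attribution, Section 10.2.2 says: "Attribution categories are as follows: Unrelated, Unlikely, Possible, Probable, and Definite". It does not say who assigns them. Section 3.3.3 states: "Due to the nature of study treatment, this is an unblinded study".

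The only analysis set in Section 13 is in 13.2 and begins: "The analysis set (evaluable subjects) consist of study-eligible subjects". It retains subjects who complete three treatments or visits plus the biopsy visit, and subjects withdrawn for progression. Everyone else who stops is non-evaluable.

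**The concern.** Section 2.2 describes this as the first use of the combination laser for these carcinomas and promises to document new or concerning reactions. An unfamiliar reaction is the kind of event whose cause is hardest to judge. If it is rated unlikely or unrelated, it is recorded but does not reach the only planned table.

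The randomized control arm is the trial's one concurrent reference for events the laser did not cause. Both arms have had a diagnostic biopsy, and both have an excisional biopsy at Day 84 with a check at Day 91. A table restricted to treatment-related events sets that reference aside.

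The missing safety population is a second, separate gap. Whoever produces the table must choose a denominator, and the one definition at hand was written for response.

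**Working it through.** **1. The filter against what is collected.** Section 10.2.2 has five attribution categories. Section 13.3.3 keeps three (possible, probable, definite) and drops two (unrelated, unlikely). Section 10.1.1 and Appendix I apply no such filter, so the all-cause data will exist.

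**2. What controls can contribute.** Section 4.1 gives controls study visits and no treatment. Step 3 of Section 10.2.2 asks the assessor to "Determine whether the adverse event is related to the protocol therapy (investigational or commercial"). With no therapy given, a control event has nothing to be related to, so on the natural reading the control column is empty whatever happens to those subjects. Sections 5.4 and 11.2 use a wider target, relatedness to taking part in the study, but Section 13.3.3 does not adopt it.

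**3. Which population applies.** The relevant texts are:
- Section 13.2: evaluable subjects only. Anyone who stops for a reason other than progression, toxicity included, is out.
- Section 3.3.2.1: subjects enrolled but not treated are left out of all analyses. Read literally this removes every control, which cannot be intended because Section 13.3.2 compares response between arms.
- Sections 12.0 and 14.5: data, and a CRF, for every subject who received treatment. This points to an all-treated population but defines none.
- Section 13.3.3: silent.

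Sections 5.4 and 11.2 also disagree on related grade III non-laboratory toxicity. The first has the subject considered for removal; the second has the subject withdrawn. This decides who leaves the evaluable set.

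**4. How many subjects the choice of set affects.** Inputs from Section 13.2: 15 and 5 evaluable, three to four non-evaluable, maximum enrolment 28. Reading the allowance as per arm, 15 + 4 = 19 laser and 5 + 4 = 9 control, and 19 + 9 = 28, which reproduces the stated maximum. The lower end gives 18 + 8 = 26. (A strict 3:1 split of 28 would give 21 and 7; the control number still lies between 5 and 9.) Laser subjects outside the evaluable set are 3/18 = 16.7% to 4/19 = 21.1%, for all reasons together.

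**5. Illustration, on an assumption.** The documents give no toxicity-withdrawal rate. Let k be the number of laser subjects who stop early for toxicity. An evaluable-only table shows 0/15 such subjects whatever k is (exact two-sided 95% interval 0 to 21.8%). Counting all 19 treated:

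| k (assumed) | All treated | Exact 95% interval |
|---|---|---|
| 0 | 0/19 = 0% | 0 to 17.6% |
| 1 | 1/19 = 5.3% | 0.1 to 26.0% |
| 2 | 2/19 = 10.5% | 1.3 to 33.1% |
| 4 | 4/19 = 21.1% | 6.1 to 45.6% |

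The k = 4 row requires every expected laser dropout to be due to toxicity.

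**6. What the control column could show.** For zero events in n, the exact upper limit is 1 − 0.025^(1/n): 52.2% for n = 5 and 33.6% for n = 9. Even 4/19 against 0/9 gives a one-sided Fisher p of C(19,4)/C(28,4) = 3876/20475 = 0.19.

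**The case against.** The strongest reply is that the filter affects one table only. All events are still asked about and documented in both arms, reported under institutional policy (Section 10.3) and reviewed by the monitoring committee (Appendix III). Possible relatedness is enough to be counted, and the anticipated reactions are local to the laser site and unlikely to be called unrelated. Open-label delivery is unavoidable, and a new table does not change who attributes. With so few controls the comparison carries little information. All of this stands, and it limits the stakes. But oversight during the trial does not replace the analysis of a stated objective, and an all-cause table does not depend on attribution at all.

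A reader might go further and infer that the plan removes toxicity withdrawals, and so the worst events, from the safety table. The documents do not say this. The evaluable set sits in the sample-size section and is built around response, Section 13.3.3 does not invoke it, and Sections 12.0 and 14.5 point towards all treated subjects. A withdrawal under Section 11.2 is by definition for a related event, so it passes the attribution filter.

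Nor can the expected dropouts be read as toxicity. Section 13.2 allows the same number in the untreated arm, which suggests general attrition.

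That attribution will be made by an unblinded investigator is likewise an inference, from the open-label design and the absence of any described adjudicator.

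**Conclusion.** The concern holds in two parts. First, the attribution filter is explicit: the sole secondary objective is analysed on three of five attribution categories, under open-label judgement, in a form that cannot display control-arm background events. This needs no numerical assumption beyond reading treatment in Section 13.3.3 as the laser.

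Second, the safety population is undefined. This is an omission, not a planned exclusion. Its effect depends on which set is used and on an unknown number of toxicity withdrawals: none if there are none, and at most 0/15 shown in place of 4/19 under the extreme assumption in the table above.

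Neither part touches the primary efficacy analysis. It does not follow that the plan will understate laser toxicity by any particular amount, and an all-cause table would only partly separate laser effects from background in a trial this size.

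**What to change.** - In Section 13.3.3, tabulate all adverse events by arm, CTCAE term and grade regardless of attribution, and show treatment-related events as a subset.
- Define a safety set: every subject with at least one laser session plus every control with at least one study visit, whether or not evaluable for response. Use it for the denominators.
- State that the exclusion of untreated subjects in Section 3.3.2.1 does not apply to controls.
- Reconcile Sections 5.4 and 11.2 on withdrawal for toxicity. Which rule should stand is a clinical decision for the study team.
- Describe the by-arm comparison as descriptive, with no test.

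The cost is a few sentences and one extra table. The visits already scheduled collect the data in both arms. The downside is a longer safety report that includes events plainly unconnected with the laser; the related subset keeps those apart.

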### **13.4 Data and Safety Monitoring**

#### 13.4.1 Role of the Research Team and the DSMC

The Research Team will continually monitor study accruals, toxicities, and responses to treatment with 595/1064 nm laser. In addition, the UM/Sylvester Comprehensive Cancer Center's Data and Safety Monitoring Committee (DSMC) will monitor this protocol according to the Cancer Center's DSM plan.

#### 13.4.2 Early stopping rule for lack of efficacy

We do not intend to stop the study early since this is a small study with the objective of gathering preliminary evidence of efficacy of the treatment arm.

### 13.5 Reporting and Exclusions

All non-identifying relevant study data will be reported to an appropriate scientific journal. Any data that meets the predefined requirements for study exclusion will be reported as long as it does not contain subject specific identification.

## 14.0 INVESTIGATOR'S RESPONSIBILITIES

### 14.1 Investigator Responsibility/Performance

The investigator will ensure that this study is conducted in accordance with all regulations governing the protection of human subjects.

The investigator will ensure that all work and services described in or associated with this protocol will be conducted in accordance with the investigational plan, applicable regulations, and the highest standards of medical and clinical research practice.

### 14.2 Confidentiality

The investigator must ensure that each subject's anonymity will be maintained and each subject's identity will be protected from unauthorized parties. A number will be assigned to each subject upon study entry and the number and the subject's initials will be used to identify the subject for the duration of the study. The investigator will maintain all documents related to this study in strict confidence.

### 14.3 Informed Consent and Permission to Use Protected Health Information

It is the responsibility of the investigator to obtain written informed consent from each subject participating in this study after adequate explanation, in

lay language, of the methods, objectives, anticipated benefits, and potential hazards of the study. The investigator must also explain that the subject is completely free to refuse to enter the study or to discontinue participation at any time (for any reason) and receive alternative conventional therapy as indicated. Prior to study participation, each subject will sign an IRB approved informed consent form and receive a copy of same (and information leaflet, if appropriate). For subjects not qualified or able to give legal consent, consent must be obtained from a parent, legal guardian, or custodian.

The investigator or designee **must** explain to the subject before enrollment into the study that for evaluation of study results, the subject's protected health information obtained during the study may be shared with the study sponsor, regulatory agencies, and the IRB. It is the investigator's (or designee's) responsibility to obtain permission to use protected health information per HIPAA from each subject, or if appropriate, the subjects' parent or legal guardian.

#### **14.4 Source Documentation and Investigator Files**

The investigator must maintain adequate and accurate records to fully document the conduct of the study and to ensure that study data can be subsequently verified. These documents should be classified into two separate categories: (1) investigator study file and (2) subject clinical source documents that corroborate data collected on the CRF's. Subject clinical source documents would include hospital/clinic patient records; physician's and nurse's notes; appointment book; original laboratory, ECG, EEG, radiology, pathology, and special assessment reports; pharmacy dispensing records; subject diaries; signed informed consent forms; and consultant letters. When the CRF or any form is used as the source document, this must be clearly stated in the investigator study file.

Minimally, the following be documented in source documents:

- Medical history/physical condition and diagnosis of the subject before involvement in the study sufficient to verify protocol entry criteria
- Study number, assigned subject number, and verification that written informed consent was obtained (each recorded in dated and signed notes on the day of entry into the study)
- Progress notes for each subject visit
- Documentation of treatment
- Laboratory test results
- Adverse events (action taken and resolution)

- Condition and response of subject upon completion of or early termination from the study

#### **14.5 Recording and Processing of Data**

If using hard copies of CRF's, study center personnel will complete individual CRF's in black ink. All corrections to entered data will be made by drawing a single line through the information to be corrected without obscuring it. All corrections will be initialed, dated and explained, if necessary. **Do not use "white-out" or obscuring correction tape.** A CRF is required for every patient who received any amount of study treatment. The investigator will ensure that the CRF's are accurate, complete, legible and timely. Separate source records are required to support all CRF entries.

#### **14.6 Non-Protocol Research**

No investigative procedures other than those described in this protocol will be undertaken on the enrolled subjects without the agreement of the IRB.

#### **14.7 Ethics**

The investigator agrees to conduct the study in compliance with the protocol, current good clinical practices, and all applicable (local, FDA) regulatory guidelines and standard of ethics.

#### **14.8 Essential documents for the conduct of a clinical trial**

Essential documents are those documents with individually and collectively permit evaluation of the conduct of a trial and the quality of the data produced.

The following documents should be on file:

- CV's and license of all investigators
- IRB documentation/correspondence
- Documentation of IRB and CITI certification

### APPENDIX I: STUDY CALENDAR

Procedure	Screening	Randomization 	Day 0	Day28 (+/- 7 days)	Day 56 (+/- 7 days)	Day 84 (+/- 7 days)	Day 91 (+/- 7 days)/ Follow up visit
Written Informed Consent	X						
HIPAA	X						
Photo consent	X						
Eligibility checklist 	X						
Velos	X						
Randomization		X					
Pt and lesion characteristics 			X	X	X	X	

Treatment #1 			X				
Treatment #2 				X			
Treatment #3 					X		
Photographs are taken			X	X	X	X	
Monitoring of adverse events and concomitant medication			X	X	X	X	X
Dermatologic eval for clearance						X	
Excisional biopsy						X	

Within 3 months of initial diagnostic biopsy and within 1 week of enrollment (+ 3 days)

 Source document titled "Enrollment"

 Source document titled "Patient information"

 Or regular study visit for control arm

